13.2.2. Eczema area and severity index

Definition and derivation

The efficacy endpoint is the change in EASI score from baseline to Week 16 (quantitative parameter). It is calculated as follows:

EASI score at visit 9 – EASI score at visit 1

Missing data for this criterion will be imputed as described in section 6.3.6 for these analyses.

The change in EASI score from baseline to Week 16 is also expressed as a percentage. It is calculated as follows:

$$\frac{\text{EASI score at visit 9} - \text{EASI score at visit 1}}{\text{EASI score at visit 1}} \times 100$$

It is then binarised in two ways according to this percentage:

- Percentage of improvement greater than or equal to 75% (qualitative parameter: "Yes", "No")
- Percentage of improvement greater than or equal to 90% (qualitative parameter: "Yes", "No")

Analysis

This analysis will be performed only on participants with eczema on a part of the body other than the hands, information collected during the baseline disease assessment (Eczema away from the hands (qualitative parameter: "Yes", "No")).

Change in EASI score from baseline to last visit will be compared between Arm A and Arm B using an ANCOVA with an analysis similar to the primary endpoint.

The proportion of participants with a percentage of improvement greater than or equal to 75% or 90 % at the visit 9 will be compared between Arm A and Arm B using a two-sided stratified CMH test controlling for that factor on which the randomization is stratified. This analysis will be similar to the previous IGA analysis.

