4. STUDY OBJECTIVES

The primary objective of the study is to demonstrate that dupilumab is more effective than placebo for the treatment of patients with moderate to severe chronic hand eczema (CHE) who are resistant or intolerant to highly potent topical corticosteroids as determined by the evolution at week 16 of the modified total lesion symptom score (mTLSS) since baseline.

Secondary objectives are:

- To demonstrate that dupilumab is more effective than placebo to improve pruritus induced by CHE at week 16 as compared to baseline.
- To demonstrate that dupilumab is more effective than placebo to improve pain induced by CHE at week 16 as compared to baseline.
- To demonstrate that dupilumab is more effective than placebo to improve quality of life at week 16 as compared to baseline.
- To demonstrate that dupilumab is more effective than placebo to improve sleep loss induced by CHE at week 16 as compared to baseline.
- To demonstrate that dupilumab is more effective than placebo to induce clearance or almost clearance of CHE at week 16 as defined by the investigator and by the patient.
- To demonstrate that dupilumab is more effective than placebo to improve work productivity at week 16 as compared to baseline.
- To evaluate the efficacy of dupilumab on other parts of the body compared with placebo, in patients with eczema not limited to the hand.
- To evaluate the evolution of laboratory parameters of patients receiving dupilumab compared to those receiving placebo.
- To evaluate the safety of dupilumab as compared to placebo throughout the course of the study.

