5.2.2. Secondary endpoints

Secondary endpoints include the following:

• Evolution of pruritus associated with CHE at week 16 since baseline measured with a visual analog scale (VAS).

- Evolution of pain associated with CHE at week 16 since baseline measured with a visual analog scale.
- Improvement of quality of life at week 16 since baseline measured by Dermatology Life Quality Index (DLQI) (1) and 5-levels EQ-5D (EQ-5D-5L)(2).
- Evolution of sleep loss associated with CHE at week 16 since baseline measured with a VAS.
- Clearance or almost clearance of hand eczema at week 16 as defined by an Investigator's global assessment (IGA)(3) of 0 or 1.
- Clearance or almost clearance of hand eczema at week 16 as assessed by the Patient's global assessment (PaGa)(4) of 0 or 1.
- Improvement of work productivity at week 16 since baseline as assessed by the questionnaire Work Productivity and Activity Impairment (WPAI)(5).
- Evolution of the Eczema Area and Severity Index (EASI) at week 16 since baseline in patients who have eczema on other parts of the body than the hands(6).
- The safety throughout the course of the study (at 20 weeks since baseline) by monitoring adverse events, serious adverse events, injection site reactions.
- Evolution of laboratory parameters (full blood count and total immunoglobulin E (IgE)) at week 16 since baseline.

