11.5. ECZEMA AREA AND SEVERITY INDEX (AT BASELINE, V3, V5, V7 AND V9)

- EASI achieved (qualitative parameter: "Yes", "No")
 - o If "No", why? (qualitative parameter in plain terms)
- EASI score (quantitative parameter: from 0 (no symptoms) to 72 (multiple severe symptoms)). The result is obtained with this scoring table:

Body region		Erythema	Edema/	Excoriation	Lichenification	Region score	Multiplier	Score per boy	
			Papulation					region	
Head/neck	(+	+	+)	×	× 0.1		
Trunk	(+	+	+)	×	× 0.3		
Upper extremities	(+	+	+)	×	× 0.2		
Lower extremities	(+	+	+)	X	× 0.4		
		The final EASI score is the sum of the 4 region scores:							

- The severity of each sign (Erythema, Edema/Papulation, Excoriation and Lichenification) is assessed on a scale of 0 to 3 (qualitative parameter: 0="None", 1="Mild", 2="Moderate", 3="Severe")
- The area of involvement of each body region is assessed on a scale of 0 to 6 (qualitative parameter) based on the following table:

% involvement	0	1 - 9%	10 - 29%	30 - 49%	50 - 69%	70 - 89%	90 - 100%
Region score	0	1	2	3	4	5	6

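### Efficacy beyond the hands is to be judged on the full four-region EASI, for which the SAP states no hand exclusion, so hand improvement can count towards it

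*SAP*

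**What the plan says.** SAP section 4 sets the objective: "To evaluate the efficacy of dupilumab on other parts of the body compared with placebo, in patients with eczema not limited to the hand". It names both a set of patients and a set of body sites.

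SAP 5.2.2 lists the matching endpoint as the evolution of the EASI "at week 16 since baseline in patients who have eczema on other parts of the body than the hands". SAP 13.2.2 repeats the patient restriction: "This analysis will be performed only on participants with eczema on a part of the body other than the hands". The subset is identified by a yes/no item at baseline. Under SAP 11.2 a yes can come from the feet alone, the head and neck alone, the trunk or limbs, or the folds.

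The score is defined in SAP 11.5: "The final EASI score is the sum of the 4 region scores". One of the four rows is "Upper extremities", with multiplier 0.2. Neither 11.5 nor 13.2.2 says whether the hands are scored in that row. The total is analysed as an absolute change (ANCOVA) and as improvement of at least 75% and at least 90% (stratified CMH test). No analysis by region or without the hands is planned.

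**The concern.** The site restriction in the objective is applied to the patients but not to the measurement. Under SAP 5.1 an eligible patient has hand eczema with an IGA of 3 or 4, so each eligible patient in the EASI subset also has substantial hand disease. In the ordinary meaning of the term the hands belong to the upper extremities. Unless raters were told otherwise, the hands contribute to the score at baseline and at week 16.

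A treatment that improves the hands and does nothing elsewhere could then separate the arms on EASI change, and on the 75% and 90% thresholds in some patients. The result would be read against an objective about other body sites, and nothing else in the plan would show where the improvement came from.

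**Working it through.** **Inputs from SAP 11.5**
- Four signs per region; each "is assessed on a scale of 0 to 3", so the sign sum S runs from 0 to 12.
- "The area of involvement of each body region is assessed on a scale of 0 to 6"; 1–9% scores 1, 10–29% scores 2, 30–49% scores 3. Call this A.
- Multipliers: head/neck 0.1, trunk 0.3, upper extremities 0.2, lower extremities 0.4.

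**Formula.** EASI = sum over regions of multiplier × S × A.

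**The plan's own figure.** The stated range is "from 0 (no symptoms) to 72 (multiple severe symptoms"). Maximum = (0.1 + 0.3 + 0.2 + 0.4) × 12 × 6 = 72, which reproduces. The upper-extremity row alone can reach 0.2 × 72 = 14.4; the other three can reach 0.8 × 72 = 57.6.

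**Assumptions not in the SAP.** The hands are scored in the upper-extremity row; that row holds no other eczema; the hands give A of 1 to 3 and S of 6 to 12.

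**Hands clear, all else unchanged.** Let h = 0.2 × S × A for the hands and r = the remote EASI. Improvement = h / (h + r).
- At least 75% when h ≥ 0.75(h + r), that is r ≤ h/3.
- At least 90% when h ≥ 0.90(h + r), that is r ≤ h/9.

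| Hands | h | Unchanged remote site | r | Baseline EASI | Improvement | Threshold met |
|---|---|---|---|---|---|---|
| S 8, A 2 | 3.2 | Feet, S 2, A 1 | 0.8 | 4.0 | 80.0% | 75% |
| S 8, A 2 | 3.2 | Trunk, S 3, A 1 | 0.9 | 4.1 | 78.0% | 75% |
| S 8, A 2 | 3.2 | Head/neck, S 3, A 1 | 0.3 | 3.5 | 91.4% | 75% and 90% |
| S 8, A 1 | 1.6 | Head/neck, S 4, A 1 | 0.4 | 2.0 | 80.0% | 75% |
| S 8, A 2 | 3.2 | Feet, S 4, A 1 | 1.6 | 4.8 | 66.7% | none |
| S 8, A 1 | 1.6 | Feet, S 2, A 1 | 0.8 | 2.4 | 66.7% | none |
| S 8, A 2 | 3.2 | Trunk, S 8, A 2 | 4.8 | 8.0 | 40.0% | none |

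Largest unchanged remote EASI that still gives a responder, for S from 6 to 12:

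| Hand area score | 75% threshold (h/3) | 90% threshold (h/9) |
|---|---|---|
| 1 | 0.40 to 0.80 | 0.13 to 0.27 |
| 2 | 0.80 to 1.60 | 0.27 to 0.53 |
| 3 | 1.20 to 2.40 | 0.40 to 0.80 |

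**Incomplete clearance.** In the first row of the examples, if the hand contribution falls by 75% rather than 100%, the improvement is 0.75 × 3.2 / 4.0 = 60%, below the threshold.

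**Continuous change.** In the last row of the examples no threshold is met, yet the EASI change is −3.2 with no remote site improved.

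**Same patient without the upper-extremity row.** In the first row of the examples the three-region score is 0.8 at baseline and 0.8 at week 16: change 0, not a responder.

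**The case against.** **The SAP does not say that the hands are scored.** This stands. Their inclusion is inferred from the name of the row and the absence of any exclusion. Scoring instructions may sit in the protocol or eCRF, on which SAP section 3 says the plan is based, and neither is at hand. The point is therefore conditional.

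**The plan analyses the endpoint it lists.** Also true: 13.2.2 follows 5.2.2, and the mismatch is with the objective in section 4. That argues against replacing the full EASI; it does not turn the full EASI into a measure of remote sites.

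**Responder status from the hands alone needs particular conditions.** It needs limited remote eczema and complete or nearly complete hand clearance, and three of the seven examples miss the threshold. A reader might infer that hand clearance generally produces a 75% response; the arithmetic does not support that. The continuous change has no such condition.

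**The EASI does not duplicate the primary endpoint.** Scaling, vesicles and fissures count in the mTLSS and are not EASI signs. The overlap is partial.

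**The analysis is exploratory.** SAP 6.2 and 13.2 disclaim confirmatory claims for it. This limits the consequence, but a hand effect is still not evidence about other sites.

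**Dropping the row loses relevant disease.** Arm and elbow-fold eczema is covered by the objective. A reader might conclude that the three-region score should become the main one; for this reason it should be added and not substituted.

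**Conclusion.** The objective and the measurement do not match. The plan restricts the patients to those with remote eczema but leaves the score open to the hands. If the hands are scored in the upper-extremity row, a hand-only effect can move the EASI change whatever the extent of remote disease. It can also create 75% responders where remote EASI is at most one third of the hand contribution, and 90% responders where it is at most one ninth. The patient values are illustrative. The share of trial patients in these ranges cannot be obtained from the SAP.

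A reader might go further and say that the analysis cannot answer the objective at all. The document does not support that: where remote disease is extensive, the remote regions dominate the total, and the hands may turn out not to have been scored. What is supported is narrower: the full EASI alone should not be read as evidence of efficacy beyond the hands. The endpoint is secondary and exploratory, and the primary conclusion does not depend on it.

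**What to change.** In SAP 13.2.2:
- Keep the full EASI as the listed endpoint, and label it as overall eczema including the hands.
- Add, for the same patients and with the same ANCOVA, the change in a three-region EASI: head/neck, trunk and lower extremities, range 0 to 57.6.
- Add 75% and 90% improvement in this score, with the same stratified CMH test, among patients whose three-region score is above 0 at baseline.
- State that a conclusion about efficacy beyond the hands requires the three-region result to agree with the full EASI.

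If the hands were in fact left out of the upper-extremity row at scoring, one sentence in SAP 11.5 saying so replaces all of this.

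The cost is one derived variable and a few lines of text, with no new data if the region components are stored. The table in 11.5 and the item-level missing-data rules in 6.3.6 suggest that they are. The change is best made before unblinding. The added score omits arm eczema outside the hands. Patients whose only remote eczema is there have a baseline of 0: they drop out of the responder analysis and dilute the change analysis, so fewer patients inform the result.

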13.2.3. Dermatology life quality index

Definition and derivation

The efficacy endpoint is the change in DLQI score from baseline to Week 16 (quantitative parameter). It is calculated as follows:

Missing data for this criterion will be imputed as described in section 6.3.6 for these analyses.

This score is then binarised according to the improvement from baseline, separating participants with an improvement of 4 or more from the others (qualitative parameter), which corresponds to the Minimal Clinically Important Difference (MCID) of the DLQI (16).

The DLQI score at the visit 9 is also used in binary form as described in section 11.6.

Analyses

Change in DLQI score from baseline to the visit 9 will be compared between Arm A and Arm B using an ANCOVA with an analysis similar to the primary endpoint.

The proportion of participants with an improvement of 4 or more at the visit 9 and the participants with a DLQI score of 0 or 1 at the visit 9 will be compared between Arm A and Arm B using a two-sided stratified CMH test controlling for that factor on which the randomization is stratified. These analyses will be similar to the previous IGA analysis.

13.2.4. 5-Level EQ-5D

Definition and derivation

The EQ-5D-5L questionnaire consists of two parts. The first with qualitative data, the second (EQ-VAS) with quantitative data.

On the first part, the 5 components of the EQ5D-5L will be evaluated for each component by comparing the changes between the baseline results and the results at the visit 9 (qualitative parameter). Changes will be categorized in relation to the baseline, as described in the form associated with the questionnaire (2):

- Their health status (for the respective component) is better
- Their health status has worsened
- Their health status remains the same

A variable summarizing this information, proposed by the creators of the questionnaire (2), will then be used: an EQ-5D health state is deemed to be "better" than another if it is better on at least one dimension and is no worse in any other dimension. An EQ-5D health state is deemed to be "worse" than another if it is worse in at least one dimension and is no better in any other dimension. Using that principle to compare a patient's EQ-5D health states between baseline and the visit 9, we get four possibilities (qualitative parameter: "Better", "Worse", "Exactly the same", "Mixed: better on one dimension, worse on another"). This last variable will then be binarized for analysis (qualitative parameter: "Improvement", "No improvement"), separating participants with an improvement ("Better") from those without ("Worse", "Exactly the same", "Mixed: better on one dimension, worse on another").

On the second part, the efficacy endpoint is the change in EQ-VAS from baseline to Week 16 (quantitative parameter). It is calculated as follows:

Missing data for this criterion will be imputed as described in sections 6.3.6 for this analysis.

Analyses

The assessment of the 5 components of the EQ-5D-5L will be conducted for each component by comparing changes between baseline results and results at the visit 9. The comparison of proportions for each category between the two arms will be performed using the appropriate bivariate test according to the expected numbers of each modality, with a type I error significance level of 0.05.

Next, the variable summarizing the information on the evolution of the 5 components of the EQ-5D-5L in two modalities described above will be analyzed. The proportion of participants with an overall improvement in EQ5D components from baseline to the visit 9 will be compared between Arm A and Arm B using a two-sided stratified CMH test controlling for that factor on which the randomization is stratified. This analysis will be similar to the previous IGA analysis.

Change in EQ-VAS from baseline to the visit 9 will be compared between Arm A and Arm B using an ANCOVA with an analysis similar to the primary endpoint.

13.2.5. Work productivity and activity impairment questionnaire

Each WPAI outcome, described in section 11.8 (work time missed, impairment while working due to health, overall work impairment due to health and activity impairment due to health) will be analyzed independently but using the same procedure.

Definition and derivation

The efficacy endpoints are the change in WPAI outcomes from baseline to Week 16 (quantitative parameter in percent). It is calculated as follows:

WPAI outcome at visit 9 – WPAI outcome at visit 1

Missing data for this criterion will be imputed as described in section 6.3.6 for these analyses.

Analyses

Change in WPAI outcomes from baseline to the visit 9 will be compared between Arm A and Arm B using an ANCOVA with an analysis similar to the primary endpoint.

13.2.6. Patient's global assessment of disease severity

Definition and derivation

The efficacy endpoint is based on PaGa score at the visit 9. The test result is binarized as described in section 11.9.

Missing data for this criterion will be imputed as described in section 6.3.8 for these analyses.

Analysis

The proportion of participants with a PaGa score of 0 or 1 at the visit 9 will be compared between Arm A and Arm B using a two-sided stratified CMH test controlling for that factor on which the randomization is stratified. This analysis will be similar to the previous IGA analysis.

13.2.7. VAS for pruritus, pain and sleep loss

Each VAS (pruritus, pain and sleep loss) will be analyzed independently but using the same procedure.

Definition and derivation

The efficacy endpoints are the change in each VAS score from baseline to the visit 9 (quantitative parameter). It is calculated as follows:

VAS score at visit 9 – VAS score at visit 1

Missing data for this criterion will be imputed as described in section 6.3.6 for these analyses.

These score are then binarised according to the improvement from baseline, separating participants with an improvement of 40 or more from the others (qualitative parameter) for VAS scores for pruritus (17), an improvement of 30 or more for VAS score for pain (18), an improvement of 40 or more for VAS score for sleep loss (19), which correspond to the MCID of these VAS.

Analyses

Change in EVA score from baseline to the visit 9 will be compared between Arm A and Arm B using an ANCOVA with an analysis similar to the primary endpoint.

The proportions of participants with VAS scores greater than or equal to will be compared between Arm A and Arm B using a two-sided stratified CMH test controlling for that factor on which the randomization is stratified. This analysis will be similar to the previous IGA analysis.

13.2.8. Laboratory parameters

Each laboratory parameters (haemoglobin, platelets, leukocytes, eosinophils, Immunoglobulin E) will be analyzed independently but using the same procedure.

Definition and derivation

The efficacy endpoints are the change in each level laboratory parameter from baseline (visit 1 for IGEs, inclusion visit for others) to Week 16 (quantitative parameter). It is calculated as follows:

level laboratory parameter at visit 9 – level laboratory parameter at visit 1 or inclusion

Missing data for this criterion will be imputed as described in section 6.3.6 for these analyses.

Analyses

Change in level laboratory parameter from baseline to the visit 9 will be compared between Arm A and Arm B using an ANCOVA with an analysis similar to the primary endpoint.

14. SAFETY ANALYSIS

Analyses will be carried out on the Treated population in the group of treatment corresponding to the treatment actually received, which may differ from the randomization arm in case of error. Analyses will be performed, in a descriptive manner, using appropriate statistics as described in Section 6.1; no statistical test will be performed. Results will be provided by arm; no result on the pooled data across the two arms will be provided.

14.1. PERIODS OF ANALYSIS

The safety analysis runs from the start of the study to the end of the study (Week 20 visit).

14.2. ADVERSE EVENTS

Analysis will be based on data recorded on "Adverse event" eCRF forms.

All expected or unexpected serious adverse events (AE), adverse event of special interest (AESI) (Conjunctivitis), and all unexpected non-serious adverse events, occurring from the date of consent signature, during the study duration, have been collected and documented on an AE form after coding according to the standardized MedDRA medical dictionary.

Thus, the incidences per group of each type of AE according to the Preferred Term (PT) will be presented and organized by System-Organ Class (SOC). If a subject had multiple AEs of the same PT, only one will be counted, so the denominator will be the number of treated subjects and the numerator the number of subjects experiencing at least one AE of that type. The same descriptive table will be presented for serious AEs and for AEs whose causality to the study or treatment is not excluded. Percentages of subjects with at least one AE, at least one serious AE, and at least one AE for which causality to the study or treatment is not excluded will be calculated with exact 95% CI.

A listing of all serious AEs and AESIs will be produced based on the treatment actually received and will contain the following informations:

- Subject and center identifier
- Date of first study treatment administration
- Date of last study treatment administration
- Date and time of the start of the AE
- Date and time of the end of the AE (or mention of the persistence of the adverse event)
- Description of the event ("Reported Term" and "Preferred Term")
- Severity, intensity
- Causality to the trial or trial treatment
- Action on the trial treatment
- Other action and evolution

The following will be presented by arm (Placebo / Dupilumab):

- The incidence of AE and AESIs based on their causality and severity
- The incidence of AE and AESIs leading to the cessation of trial treatment
- AEs and AESIs occurring between the consent signature and the first administration of treatment

In addition to these safety analyses, the percentage of patients reporting injection site reactions will also be presented overall and by group with exact 95% CI together.

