6.3.10. Handling of missing/incomplete dates for adverse events

In case of completely missing or incomplete AE onset date, an imputed AE onset date is calculated in order to derive AE treatment-emergence and AE period-occurrence statuses in any. Always one and the same imputation rule is used, that is, in order not to miss any AEs that occur or may have occurred from the first study treatment administration, imputation rule sets missing/incomplete onset date to the date of the first study treatment administration if another date is not obvious, otherwise "as early as possible" (see details below).

In case of completely missing or incomplete AE end date, an imputed AE end date is derived to help for imputation of missing/incomplete AE onset date, if any, so that inconsistency in the chronology of the dates does not arise (see details below).

Of note, imputed AE onset and end dates are for treatment-emergence/period-occurrence status categorization purpose only; they will neither be used to compute other information on AEs, such as duration, nor be displayed in any individual data listing.

Imputation of AE end date

For AEs that are not "ongoing", as reported by investigators on the adverse event forms, missing/incomplete end dates are handled as follows:

- In case of completely missing end date, missing end date is imputed by the date of the patient's end-of-study derived as the latest date among the date of premature withdrawal from study as reported in the "Early study discontinuation" eCRF form (if any) and the date of last study visit performed.
- In case of incomplete end date with both missing day and month parts, missing end day/month is imputed by 31 December.
- In case of incomplete end date with only missing day part, missing end day is imputed by the last day of the month.

Imputation of AE onset date

Missing/incomplete AE onset dates are handled as follows:

- In case of completely missing onset date:
 - o If AE end date (after being imputed as above where necessary) is after or equal to the date of the first study treatment administration, missing onset date is imputed by the date of the first study treatment administration.
 - If AE end date (after being imputed as above where necessary) is prior to the date of the first study treatment administration, missing onset date is imputed by the date of the patient's informed consent signature.
- In case of incomplete onset date with both missing day and month parts:

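### The main adverse-event tables count events from consent, so events before any dose enter each arm's incidence and modestly dilute the contrast

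*SAP*

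**What the plan says.** - SAP 14.1 sets the period: "The safety analysis runs from the start of the study to the end of the study (Week 20 visit"). Section 5.1 names screening as the first of the three study phases, so the start of the study lies before the first dose.
- SAP 14.2 lists what was collected: serious events whether expected or not, conjunctivitis as the event of special interest, "and all unexpected non-serious adverse events, occurring from the date of consent signature, during the study duration".
- The same section defines the SOC/PT tables over the Treated population: "the denominator will be the number of treated subjects and the numerator the number of subjects experiencing at least one AE of that type". Serious AEs and AEs possibly related to the study or treatment get tables of the same format.
- The headline figures, with exact 95% intervals, are given as "Percentages of subjects with at least one AE, at least one serious AE, and at least one AE for which causality"; the last of these covers AEs that may be related to the study or the drug.
- SAP 14.2 also calls for AEs and AESIs between consent and first administration to be presented by arm.
- SAP 6.3.10 imputes missing or partial onset dates "in order to derive AE treatment-emergence and AE period-occurrence statuses".
- SAP 5.2.2 states the safety endpoint over 20 weeks counted from baseline.

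**The concern.** Followed literally, the plan counts an event in the screening period towards the arm of the treatment received later. It cannot be an effect of that treatment. Such events should be balanced by randomisation, so they add about the same amount to both arms and pull the relative contrast towards no difference. The possibly-related table is also open to this, because it admits causality to the study as well as to the drug, so a pre-dose event ascribed to a study procedure would count in an arm.

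The plan is also inconsistent with itself. It defines the endpoint from baseline, prepares a treatment-emergence status, analyses safety by treatment actually received, and then sets no onset condition in the tables that carry the safety comparison. Safety against placebo is a stated secondary objective (section 4), so a reader will take these percentages as incidence on treatment.

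**Working it through.** **1. Is there an onset condition anywhere in the main tables?**

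| Place in the SAP | Time origin |
|---|---|
| 5.2.2, safety endpoint | baseline, to 20 weeks |
| 6.3.10, onset imputation | first administration (treatment-emergence) |
| 14.1, analysis period | start of the study, to week 20 |
| 14.2, events collected | consent |
| 14.2, SOC/PT tables and headline percentages | none stated; built on the events collected |
| 14.2, separate presentation | consent to first administration |

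The split at first dose is used only for the last row. No sentence removes those events from the main numerators.

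**2. Share of the counted time that is before any dose.**

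Inputs from section 5.1: screening 1 to 4 weeks before treatment, treatment 16 weeks, follow-up 4 weeks. Assumption: consent is signed at screening. Post-dose time is 16 + 4 = 20 weeks.

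- 1 week: 1 / (1 + 20) = 1/21 = 4.8%
- 4 weeks: 4 / (4 + 20) = 4/24 = 16.7%

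**3. Dilution of a rate ratio.**

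The SAP gives no AE rates, so this is an illustration. Assume a constant background rate of 1 per week on placebo and before dosing, and twice that on dupilumab after dosing. With s pre-dose weeks, the apparent ratio is (2 × 20 + s) / (20 + s).

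- s = 1: 41/21 = 1.95
- s = 4: 44/24 = 1.83

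**4. The same on the planned metric, patients with at least one event.**

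Assume post-dose proportions of 50% on placebo and 65% on dupilumab. The pre-dose proportion at the placebo hazard is q = 1 − (1 − 0.50)^(s/20), and the counted proportion is 1 − (1 − p)(1 − q).

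| Pre-dose weeks | q | Placebo | Dupilumab | Difference |
|---|---|---|---|---|
| none | 0 | 50.0% | 65.0% | 15.0 points |
| 1 | 0.034 | 51.7% | 66.2% | 14.5 points |
| 4 | 0.129 | 56.5% | 69.5% | 13.1 points |

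Both percentages rise and the difference shrinks by 0.5 to 1.9 points under these assumptions.

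**The case against.** The strongest reply is that section 14.2 already asks for pre-dose events by arm. That table cannot be made without dividing events at first dose, so the safety section does use the split, and a reader can see the pre-dose events. This stands as far as it goes: section 14 cannot be said to ignore the distinction. But the table is an additional presentation, and the main numerators are left unchanged.

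It is also fair that the effect is small, that section 14 is descriptive with no tests, and that some outputs are largely insulated: an AE leading to cessation of treatment presupposes that treatment had begun. These points limit the importance without removing the inconsistency.

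A reader might infer two stronger things:

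- **That omitting expected non-serious events makes dupilumab look safer.** Apart from conjunctivitis, such events are absent from the list in 14.2. But the SAP does not define expectedness or name a reference list, so neither the direction nor the size of any effect on the arm comparison can be established. The text reports what was collected, a rule that may come from the protocol, and it states the restriction immediately before the tables. What remains is a labelling point.
- **That injection site reactions went unrecorded.** Section 14.2 says that "the percentage of patients reporting injection site reactions will also be presented overall and by group", in addition to the other safety analyses, and 5.2.2 names them separately. Their source is not spelled out, but nothing shows that they are missing.

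**Conclusion.** The point holds for the time window. As written, the SOC/PT tables and the AE, serious-AE and possibly-related-AE percentages include events before any dose, against the plan's own baseline-anchored endpoint and without the treatment-emergence status it derives. Between 4.8% and 16.7% of the counted time is pre-dose if consent is taken at screening.

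The resulting dilution is modest: an assumed rate ratio of 2.0 becomes 1.95 to 1.83, and an assumed 15.0-point difference becomes 14.5 to 13.1 points. Both rest on assumed rates, a constant hazard and a pre-dose hazard equal to that on placebo. The dilution would not by itself overturn a safety conclusion, but correcting it costs almost nothing.

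The label on the at-least-one-AE percentage is a lesser matter: it should say which event types it covers, so that it is not read as overall AE incidence. No claim of directional bias from the collection rule, or of missing injection site reactions, is supported.

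**What to change.** - In 14.1 and 14.2, restrict the main SOC/PT, serious-AE and possibly-related-AE tables, and the percentages with exact intervals, to events with onset on or after first administration through week 20. Use the onset rule of 6.3.10, which assigns undetermined onsets to the first-administration date unless another date is evident, so doubtful events stay in.
- Keep the consent-to-first-administration presentation as a separate table, and state that its events are not in the main numerators.
- As a minor accompanying change, title the tables and the at-least-one-AE percentage by what was recorded: serious AEs, the AESI (conjunctivitis) and unexpected non-serious AEs.

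The cost is a few sentences in the SAP and one date filter in the AE programs. No new data are needed and no event is lost from the report, since pre-dose events remain in their own table.
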